# Hyperkyphosis Clinic Screening Exam

Please complete the survey below.

Thank you!

Participant ID

---

Acrostic

---

Interviewer

---

Was blood pressure measured?

Yes  
 No

Enter value: Systolic:

---

Diastolic:

---

Was Resting heart rate measured?

Yes  
 No

Enter value: Resting heart rate:

---

Gender

Male  
 Female

Age of menopause:

---

Current or prior hormone replacement

Yes  
 No

Prior chronic glucocorticoid use (> 3 months in a row in the past year)

Yes  
 No

Have you ever smoked cigarettes?

Never  
 Yes

Current smoker

- Yes
- No

Past smoker

- Yes
- No

Do you currently drink alcohol (more than 1 drink a month)?

- Yes
- No

Average number of drinks/week

---

History of fracture

- Yes
- No

Where:

- spine
- hip
- arm
- leg
- other

Biological parent fractured a hip?

- Yes
- No
- Don't know

Biological parent had stooped posture?

- Yes
- No
- Don't know

Which parent?

- mother
- father

Current or past osteoporosis medication use

- Yes
- No
- Don't know

current or prior use?

- current
- prior

Do you have chest pain on exertion?

- Yes
- No
- I don't know

Shortness of breath on exertion

- Yes
- No
- I don't know

Joint pain or arthritis

- Yes
- No

what joint?

- shoulder
- elbow
- wrist/hand
- neck
- back
- hip
- knee
- ankle
- jaw

# Hyperkyphosis Medical History

Please complete the survey below.

Thank you!

Participant ID

---

Acrostic

---

Interviewer

---

Have you ever been diagnosed with any of the following conditions?

Heart attack

- Yes
- No
- Don't know

Year of diagnosis:

---

Are you currently under a physician's care for this?

- Yes
- No

Transient ischemic attack

- Yes
- No
- Don't know

Year of diagnosis:

---

Are you currently under a physician's care for this?

- Yes
- No

Stroke

- Yes
- No
- Don't know

Year of diagnosis:

---

Are you currently under a physician's care for this?

- Yes
- No

High blood pressure

- Yes
- No
- Don't know

Year of diagnosis:

---

Are you currently under a physician's care for this?

- Yes
- No

Peripheral vascular disease

- Yes
- No
- Don't know

Year of diagnosis:

---

Are you currently under a physician's care for this?

- Yes
- No

Diabetes

- Yes
- No
- Don't know

Year of diagnosis:

---

Are you currently under a physician's care for this?

- Yes
- No

Kidney disease

- Yes
- No
- Don't know

Year of diagnosis:

---

Are you currently under a physician's care for this?

- Yes
- No

Neuropathies (problems with sensation)

- Yes
- No
- Don't know

Year of diagnosis:

---

Are you currently under a physician's care for this?

- Yes
- No

Respiratory disease including asthma

- Yes
- No
- Don't know

Year of diagnosis:

---

Are you currently under a physician's care for this?

- Yes
- No

Parkinson's disease

- Yes
- No
- Don't know

Year of diagnosis:

---

Are you currently under a physician's care for this?

- Yes
- No

Multiple sclerosis

- Yes
- No
- Don't know

Year of diagnosis:

---

Are you currently under a physician's care for this?

- Yes
- No

Polio/post-polio syndrome

- Yes
- No
- Don't know

Year of diagnosis:

---

Are you currently under a physician's care for this?

- Yes
- No

Epilepsy/seizures

- Yes
- No
- Don't know

Year of diagnosis:

---

Are you currently under a physician's care for this?

- Yes
- No

Cancer

- Yes
- No
- Don't know

what kind?

- breast
- prostate
- bladder
- colon/rectal
- endometrial
- kidney (renal cell)
- leukemia
- lung
- melanoma
- non-Hodgkin lymphoma
- pancreatic
- thyroid
- other

Year of diagnosis:

---

Are you currently under a physician's care for this?

- Yes
- No

Osteoporosis

- Yes
- No
- Don't know

Year of diagnosis:

---

Are you currently under a physician's care for this?

- Yes
- No

Rheumatoid arthritis

- Yes
- No
- Don't know

Year of diagnosis:

---

Are you currently under a physician's care for this?

- Yes
- No

Osteoarthritis/joint pain

- Yes
- No
- Don't know

where?

- neck
- back
- shoulder
- elbow
- wrist/hand
- hip
- knee
- foot/ankle
- other

Osteoarthritis: neck:

what is average level of pain

- 0 (none)
- 1
- 2
- 3
- 4
- 5
- 6
- 7
- 8
- 9
- 10 (worst imaginable pain)

Osteoarthritis: neck:

does it interfere with basic activities of daily living (including dressing, eating, walking, toileting, hygiene)

- Yes
- No

Osteoarthritis: neck:

does it interfere with instrumental activities of daily living (including shopping, housekeeping, accounting, food preparation, telephone/transportation)

- Yes
- No

Osteoarthritis: back:

what is average level of pain

- 0 (none)
- 1
- 2
- 3
- 4
- 5
- 6
- 7
- 8
- 9
- 10 (worst imaginable pain)

Osteoarthritis: back:

does it interfere with basic activities of daily living (including dressing, eating, walking, toileting, hygiene)

Yes  
 No

Osteoarthritis: back:

does it interfere with instrumental activities of daily living (including shopping, housekeeping, accounting, food preparation, telephone/transportation)

Yes  
 No

Osteoarthritis: shoulder:

what is average level of pain

0 (none)  
 1  
 2  
 3  
 4  
 5  
 6  
 7  
 8  
 9  
 10 (worst imaginable pain)

Osteoarthritis: shoulder:

does it interfere with basic activities of daily living (including dressing, eating, walking, toileting, hygiene)

Yes  
 No

Osteoarthritis: shoulder:

does it interfere with instrumental activities of daily living (including shopping, housekeeping, accounting, food preparation, telephone/transportation)

Yes  
 No

Osteoarthritis: elbow:

what is average level of pain

0 (none)  
 1  
 2  
 3  
 4  
 5  
 6  
 7  
 8  
 9  
 10 (worst imaginable pain)

Osteoarthritis: elbow:

does it interfere with basic activities of daily living (including dressing, eating, walking, toileting, hygiene)

Yes  
 No

Osteoarthritis: elbow:

does it interfere with instrumental activities of daily living (including shopping, housekeeping, accounting, food preparation, telephone/transportation)

Yes  
 No

Osteoarthritis: wrist/hand:

what is average level of pain

0 (none)  
 1  
 2  
 3  
 4  
 5  
 6  
 7  
 8  
 9  
 10 (worst imaginable pain)

Osteoarthritis: wrist/hand:

does it interfere with basic activities of daily living (including dressing, eating, walking, toileting, hygiene)

Yes  
 No

Osteoarthritis: wrist/hand:

does it interfere with instrumental activities of daily living (including shopping, housekeeping, accounting, food preparation, telephone/transportation)

Yes  
 No

Osteoarthritis: hip:

what is average level of pain

0 (none)  
 1  
 2  
 3  
 4  
 5  
 6  
 7  
 8  
 9  
 10 (worst imaginable pain)

Osteoarthritis: hip:

does it interfere with basic activities of daily living (including dressing, eating, walking, toileting, hygiene)

Yes  
 No

Osteoarthritis: hip:

does it interfere with instrumental activities of daily living (including shopping, housekeeping, accounting, food preparation, telephone/transportation)

Yes  
 No

Osteoarthritis: knee:  
what is average level of pain

- 0 (none)
- 1
- 2
- 3
- 4
- 5
- 6
- 7
- 8
- 9
- 10 (worst imaginable pain)

Osteoarthritis: knee:  
does it interfere with basic activities of daily living (including dressing, eating, walking, toileting, hygiene)

- Yes
- No

Osteoarthritis: knee:  
does it interfere with instrumental activities of daily living (including shopping, housekeeping, accounting, food preparation, telephone/transportation)

- Yes
- No

Osteoarthritis: foot/ankle:  
what is average level of pain

- 0 (none)
- 1
- 2
- 3
- 4
- 5
- 6
- 7
- 8
- 9
- 10 (worst imaginable pain)

Osteoarthritis: foot/ankle:  
does it interfere with basic activities of daily living (including dressing, eating, walking, toileting, hygiene)

- Yes
- No

Osteoarthritis: foot/ankle:  
does it interfere with instrumental activities of daily living (including shopping, housekeeping, accounting, food preparation, telephone/transportation)

- Yes
- No

Osteoarthritis: other:  
what is average level of pain

- 0 (none)
- 1
- 2
- 3
- 4
- 5
- 6
- 7
- 8
- 9
- 10 (worst imaginable pain)

Osteoarthritis: other:  
does it interfere with basic activities of daily living (including dressing, eating, walking, toileting, hygiene)

- Yes
- No

Osteoarthritis: other:  
does it interfere with instrumental activities of daily living (including shopping, housekeeping, accounting, food preparation, telephone/transportation)

- Yes
- No

Year of diagnosis:

---

Are you currently under a physician's care for this?

- Yes
- No

Degenerative disc disease

- Yes
- No
- Don't know

where?

- neck
- back

Year of diagnosis:

---

Are you currently under a physician's care for this?

- Yes
- No

Joint replacement surgery

- Yes
- No
- Don't know

which joint?

- shoulder
- hip
- knee
- other

Year of diagnosis:

---

Are you currently under a physician's care for this?

- Yes
- No

Prior spine surgery

- Yes
- No
- Don't know

what type?

- spinal fusion
- laminectomy
- foramenotomy
- other

Year of diagnosis:

---

Are you currently under a physician's care for this?

- Yes
- No

Scoliosis

- Yes
- No

Year of diagnosis

---

Are you currently under a physician's care for this?

- Yes
- No

Cerebellar problems (ataxia)

- Yes
- No
- Don't know

Year of diagnosis:

---

Are you currently under a physician's care for this?

- Yes
- No

Chemical dependency (alcohol or drugs)

- Yes
- No
- Don't know

Year of diagnosis:

---

Are you currently under a physician's care for this?

- Yes
- No

Depression

- Yes
- No
- Don't know

Year of diagnosis:

---

Are you currently under a physician's care for this?

- Yes
- No

Post traumatic stress disorder (PTSD)

- Yes
- No
- Don't know

Year of diagnosis:

---

Are you currently under a physician's care for this?

- Yes
- No

Latex allergy

- Yes
- No
- Don't know

Year of diagnosis:

---

Are you currently under a physician's care for this?

- Yes
- No

Was time to walk over 4 m course collected?

- Yes
- No

Time to walk over a 4 meter course:

---

(seconds)

why not?

- Participant refused
- Participant unable

Was usual Kyphosis measured?

- Yes
- No

record :

---

(degrees)

why not?

- Participant refused
- Participant unable

was Best kyphosis measured?

- Yes
- No

record:

---

why not?

- Participant refused
- Participant unable

Difference between Best and usual kyphosis:

---

Sit to stand from 16" high chair (Able to perform with arms crossed over chest)

- Yes
- No

Safety tests:

Able to transition from standing to recumbent on the floor and rise from the floor to standing

- Yes
- No

Able to lift both arms to shoulder level

- Yes
- No

Able to stand with feet side by side for 30 seconds

- Yes
- No

Able to stand with feet hip-width apart for 60 seconds.

- Yes
- No

# Hyperkyphosis Medications Inventory

Please complete the survey below.

Thank you!

Do you take medications, vitamins and supplements?

- Yes
- No

Medication allergy?

- Yes
- No

How many do you take?

- 1
- 2
- 3
- 4
- 5
- 6
- 7
- 8
- 9
- 10

Name:

---

Prescription:

- Yes
- No

Duration of use:

- < 1 month
- 1 month - 1 year
- 1 - 3 years
- 3 - 5 years
- > 5 years
- Don't know

Frequency:

- As needed
- Regular

# Hyperkyphosis Demographics

Please complete the survey below.

Thank you!

Participant ID

---

Acrostic

---

Interviewer

---

Date of birth

---

Sex

male  
 female

Ethnicity

Hispanic or Latino  
 Not Hispanic or Latino

Race (mark all that apply)

American Indian/Alaska Native  
 Asian  
 Native Hawaiian/Other Pacific Islander  
 Black or African American  
 White

Highest level of education

Some high school or less  
 High school graduate or GED or equivalent  
 Some college, vocational school (or junior college)  
 College graduate (BA, BS)  
 Professional or graduate degree (MA, MS, MBA, PhD, MD, JD, etc.)

# Hyperkyphosis Kyphosis and Strength Characteristics

Please complete the survey below.

Thank you!

Participant ID

---

Acrostic

---

Interviewer

---

Height

---

(cms)

Weight

---

(kgs)

Cobb angle of kyphosis from kyphometer - usual1

---

(degrees)

Cobb angle of kyphosis from kyphometer - usual2

---

(degrees)

Difference between Usual 1 and Usual 2

---

(degrees)

Cobb angle of kyphosis from kyphometer - usual3

---

(degrees)

Lumbar lordosis from kyphometer - usual1

---

(degrees)

Lumbar lordosis from kyphometer - usual2

---

(degrees)

Difference between Usual 1 and Usual 2

---

(degrees)

Lumbar lordosis from kyphometer - usual3

---

(degrees)

Mean lumbar lordosis from kyphometer

---

Spinal extension total work from biodex at 60 deg/s

---

(newtons)

Spinal extension peak torque/body weight from biodex at 60 deg/s

---

(%)

Spinal extension coefficient of variation at 60 deg/s

---

(%)

Spinal flexion total work from biodex at 60 deg/s

---

(newtons)

Spinal flexion peak torque/body weight from biodex at 60 deg/s

---

(%)

Spinal flexion coefficient of variation at 60 deg/s

---

(%)

Spinal extension total work from biodex at 90 deg/s

---

(newtons)

Spinal extension peak torque/body weight from biodex at 90 deg/s

---

(%)

Spinal extension coefficient of variation at 90 deg/s

---

(%)

Spinal flexion total work from biodex at 90 deg/s

---

(newtons)

Spinal flexion peak torque/body weight from biodex at 90 deg/s

---

(%)

Spinal flexion coefficient of variation at 90 deg/s

---

(%)

# Hyperkyphosis Physical performance testing

Please complete the survey below.

Thank you!

Participant ID

---

Acrostic

---

Interviewer

---

Standing Static Balance

Were the balance tests completed?

Yes  
 No

Side-by-side stand

Was participant able to hold side-by-side stand for 10 seconds?

Yes  
 No

Did the participant hold the side-by-side stand for more than 0 seconds?

Yes  
 No

Enter time:

---

(seconds)

Why wasn't the side-by-side test completed?

participant unable to hold side-by-side stand for any time  
 participant refused side-by-side test  
 side-by side test not attempted or data missing

Semi-tandem stand

Was participant able to hold semi-tandem stand for 10 seconds?

Yes  
 No

Did the participant hold the semi-tandem stand for more than 0 seconds?

Yes  
 No

Enter time:

---

(seconds)

Why wasn't the semi-tandem test completed?

- participant unable to hold semi-tandem stand for any time
- participant refused semi-tandem test
- semi-tandem test not attempted or data missing

Tandem stand

Was participant able to hold tandem stand for 10 seconds?

- Yes
- No

Did the participant hold the tandem stand for more than 0 seconds?

- Yes
- No

Enter time:

---

(seconds)

Why wasn't the tandem test completed?

- participant unable to hold tandem stand for any time
- participant refused tandem test
- tandem test not attempted or data missing

Chair Rise

Were the chair tests completed?

- Yes
- No

Was participant able to rise once without using arms?

- Yes, did not use arms
- No

Why wasn't participant able to rise once without arms?

- Used arms to stand
- Unable to rise once from chair even with arm use
- Participant refused to rise from chair once
- Rise from chair once not attempted or data missing

Was participant able to rise five times without using arms?

- Yes
- No

Enter time to complete

---

(seconds)

Why wasn't participant able to rise five times without arms?

- participant used arms to stand but completed 5 stands
- unable to complete all 5 stands (regardless of arm use)
- participant refused to rise from chair five times
- rise from chair five times not attempted or data missing

Book lift

Was participant able to complete the book lift task?

- Yes
- No

Enter time:

---

(seconds)

Why wasn't the book lift task completed?

- Participant unable to do this task
- Participant refused test
- Test not attempted or data missing

Jacket task

Was participant able to complete the jacket on/off task?

- Yes
- No

Enter time:

---

(seconds)

Why wasn't the jacket on/off task completed?

- Participant unable to do this task
- Participant refused test
- Test not attempted or data missing

Pick up penny task

Was the participant able to complete the pick up a penny from floor task?

- Yes
- No

Enter time:

---

(seconds)

Why wasn't the pick up penny task completed?

- Participant unable to do this task
- Participant refused test
- Test not attempted or data missing

Turn 360 degrees task

Was the participant able to complete the turn 360 degrees task?

- Yes
- No

Why wasn't the turn 360 degrees task completed?

- Participant unable to do this task
- Participant refused test
- Test not attempted or data missing

Was number of steps taken in 360 degree task collected?

- Yes
- No

How many steps were taken in the turn 360 degree task?

---

(steps)

Were the steps taken in the turn 360 degrees task discontinuous or continuous?

- Discontinuous steps
- Continuous steps
- Unable to assess steps

Was the gait in the turn 360 degrees task steady or unsteady?

- Unsteady (grabs, staggers)
- Steady
- Unable to assess gait

50-foot walk

Was the participant able to complete the 50-foot walk from floor task?

- Yes
- No

Enter time:

---

(seconds)

Why wasn't the 50-foot walk completed?

- Participant unable to do this task
- Participant refused test
- Test not attempted or data missing

4 meter walk

Was the 4 meter (13.1234 feet) task completed?

- Yes
- No

Enter time to complete

---

(seconds)

Why wasn't the 4 meter task completed?

- Participant unable to do this task
- Participant refused test
- Test not attempted or data missing

Stairs

Was the stairs task completed?

- Yes
- No

Why wasn't the stairs completed?

- Participant unable to do this task
- Participant refused test
- Test not attempted or data missing

Were number of flights climbed recorded:

- Yes
- No

How many flights of stairs were climbed?

---

(flights)

Was blood pressure measured after the stairs task?

- Yes
- No

Enter diastolic:

---

Enter systolic:

---

Was heart rate measured after stairs task?

- Yes
- No

Enter heart rate:

---

(beats per 15 seconds)

Timed up and go

Was the timed up and go test completed?

- Yes
- No

Enter time to complete

---

(seconds)

Why wasn't the timed up and go test completed?

- Participant unable to do this task
- Participant refused test
- Test not attempted or data missing

Timed loaded standing

Was the timed loaded standing test completed?

- Yes
- No

Enter time to complete

---

(seconds)

Why wasn't the timed loaded standing test completed?

- Participant unable to do this task
- Participant refused test
- Test not attempted or data missing

Six minute walk test

Was the six minute walk test completed?

- Yes
- No

enter total lengths completed

---

Feet in final lap

---

(ft.)

Total distance covered (total lengths completed x 60) + feet in final lap) =

---

(ft.)

Total distance covered in meters:

note: I can round this down to a certain number of decimal places

---

(meters)

Why wasn't the six minute walk test completed?

- Participant started unable to complete this task (could not walk for 6 minutes)
- Participant unable to walk at all
- Participant refused test
- Test not attempted or data missing

Was the time that the participant walked recorded?

- Yes
- No

enter time:

---

(minutes)

enter distance walked in that time:

---

(feet)

# Hyperkyphosis Physical Activity Survey

Please complete the survey below.

Thank you!

Participant ID:

---

Acrostic:

---

Interviewer:

---

The next few questions ask about your physical activity during the last 7 days. If the last 7 days have not been typical because of illness or bad weather, please estimate based on two or three weeks ago.

Over the past 7 days, how often did you participate in sitting activities such as reading, watching TV or doing handcrafts?

- Never
- Seldom (1-2 days)
- Sometimes (3-4 days)
- Often (5-7 days)

What were these activities?

On average, how many hours per day did you engage in these sitting activities?

- Less than 1 hour
- Between 1 and 2 hours
- 2-4 hours
- More than 4 hours

Over the past 7 days, how often did you take a walk outside your home or yard for any reason? For example, for fun or exercise, walking to work, walking the dog, etc.?

- Never
- Seldom (1-2 days)
- Sometimes (3-4 days)
- Often (5-7 days)

What were these activities?

On average, how many hours per day did you spend walking?

- Less than 1 hour
- Between 1 and 2 hours
- 2-4 hours
- More than 4 hours

Over the past 7 days, how often did you engage in light sport or recreational activities such as bowling, golf with a cart, shuffleboard, fishing from a boat or pier, or other similar activities?

- Never
- Seldom (1-2 days)
- Sometimes (3-4 days)
- Often (5-7 days)

What were these activities?

On average, how many hours per day did you engage in these light sport or recreational activities?

- Less than 1 hour
- Between 1 and 2 hours
- 2-4 hours
- More than 4 hours

Over the past 7 days, how often did you engage in moderate sport and recreational activities such as doubles tennis, ballroom dancing, hunting, ice skating, golf without a cart, softball or other similar activities?

- Never
- Seldom (1-2 days)
- Sometimes (3-4 days)
- Often (5-7 days)

What were these activities?

On average, how many hours per day did you engage in these moderate sport or recreational activities?

- Less than 1 hour
- Between 1 and 2 hours
- 2-4 hours
- More than 4 hours

Over the past 7 days, how often did you engage in strenuous sport and recreational activities such as jogging, swimming, cycling, singles tennis, aerobic exercise, skiing (downhill or cross country) or other similar activities?

- Never
- Seldom (1-2 days)
- Sometimes (3-4 days)
- Often (5-7 days)

What were these activities?

On average, how many hours per day did you engage in these strenuous sport or recreational activities?

- Less than 1 hour
- Between 1 and 2 hours
- 2-4 hours
- More than 4 hours

Over the past 7 days, how often did you do any exercise specifically to increase muscle strength and endurance, such as lifting weights or pushups, etc.?

- Never
- Seldom (1-2 days)
- Sometimes (3-4 days)
- Often (5-7 days)

What were these activities?

On average, how many hours per day did you engage in exercises to increase muscle strength and endurance?

- Less than 1 hour
- Between 1 and 2 hours
- 2-4 hours
- More than 4 hours

During the past 7 days, have you done any light housework, such as dusting or washing dishes?

- Yes
- No

During the past 7 days, have you done any heavy housework or chores, such as vacuuming, scrubbing floors, washing windows or carrying wood?

- Yes
- No

During the past 7 days, did you engage in any of the following activities? (Please answer yes or no for each item.)

Home repairs, like painting, wallpapering, electrical work, etc.?

- Yes
- No

Lawn work or yard care, including snow or leaf removal, wood chopping, etc.?

- Yes
- No

Outdoor gardening?

- Yes
- No

Caring for another person, such as children, dependent spouse, or another adult?

- Yes
- No

During the past 7 days did you work, either for pay or as a volunteer?

- Yes
- No

How many hours in the past week did you work for pay and/or as a volunteer?

---

Which of the following categories best describes the amount of physical activity required on your job and/or volunteer work?

- Mainly sitting with slight arm movements - Examples: office worker, watchmaker, seated assembly line worker, bus driver, etc.
- Sitting or standing with some walking - Examples: cashier, general office worker, light tool and machinery worker
- Walking, with some handling of materials generally weighing less than 50 pounds - Examples: mailman, waiter/waitress, construction worker, heavy tool and machinery worker
- Walking and heavy manual work often requiring handling materials weighing more than 50 pounds - Examples: lumberjack, stone mason, farm or general laborer.

# Hyperkyphosis Weekly Log

Please complete the survey below.

Thank you!

Participant ID

---

Acrostic

---

Interviewer

---

Class number:

---

Wave number:

---

Have you fallen since the last group exercise class?

- Yes
- No

how many times:

- 1
- 2
- 3 OR MORE

was it an injurious fall?

- Yes
- No

check all that apply

- Muscle strain
- Joint sprain
- bruise
- fracture
- Other

Have you had any injuries not related to a fall since the last group exercise class?

- Yes
- No

please check all that apply

- Muscle strain
- Joint sprain
- bruise
- fracture
- OTHER

Has your usual level of pain changed since the last class?

- Yes
- No

Overall average pain level in the 48hours prior to assessment at rest

- 0 - No pain
- 1
- 2
- 3
- 4
- 5
- 6
- 7
- 8
- 9
- 10 - Worst pain imaginable

Describe location: (Mark all that apply):

- arms R
- arms L
- legsR
- legs L
- shoulders R
- shoulders L
- backR
- back L
- neckR
- neck L
- head
- other

other:

---

Overall average pain level in the 48hours prior to assessment during movement

- 0 - No pain
- 1
- 2
- 3
- 4
- 5
- 6
- 7
- 8
- 9
- 10 - Worst pain imaginable

Describe location: (Mark all that apply):

- arms R
- arms L
- legsR
- legs L
- shoulders R
- shoulders L
- backR
- back L
- neckR
- neck L
- head
- other

other:

---

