## **7. SAFETY ASSESSMENTS**

### **7.1 Specification of Safety Parameters**

A Data Safety and Monitoring Board has been created to review study safety and any adverse events that may occur. The study research assistants will monitor participants during study visits and teach participants to self-monitor to prevent injury during testing and exercise sessions. Prior to each visit, participants will complete an adverse event log to monitor pain, falls, and any injuries. These will be reviewed daily by the PI and the Data Safety Monitoring Board has been established to review any adverse events.

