### **7.3 Adverse Events and Serious Adverse Events**

**Description of Adverse Event Grading and Anticipated Adverse Events:** An adverse event (AE) is here defined as any unfavorable and unintended sign, symptom, injury or disease temporarily associated with an intervention or procedure, regardless of whether it is considered related to an intervention or procedure that occurs during the course of the study. An AE may be unrelated to the experimental intervention, but nevertheless related to study participation.

The PI will assess the cause of the AE to determine whether it is definitely related, probably related, possibly related or unrelated to study participation. However, information about AE determined to be unrelated to the study participation must be retained for follow-up, documentation and reference. In this study, we do not anticipate moderate, severe, life-threatening or fatal AEs. AE will be scored as follows:

Grade 1	Mild	Transient of mild discomfort; no limitation in activity; no medical intervention or therapy required.
Grade 2	Moderate	Mild to moderate limitation in activity - some assistance may be needed; simple therapeutic intervention/therapy may be required.
Grade 3	Severe	Results in inability to carry on normal activities and required professional medical attention, hospitalization possible.
Grade 4 and/or	Life-threatening	Extreme limitation in activity, significant assistance required, results in an immediate risk of death results in persistent or Significant disability.

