## 7.6 Safety Monitoring

The DSMB will make decisions based on pre-specified guidelines detailed below. Decision-making will explicitly include consideration of both statistical and non-statistical issues.

Subjects will have an opportunity to privately discuss any musculoskeletal or other physical complaints due to study exercise with a member of the research study staff on a weekly basis at the beginning of an exercise session. Participants will also have a contact number to report any potential adverse events that occur in between scheduled study visits. We will monitor participants during the study visits, and teach participants to self-monitor during study visits to prevent injury during the testing or exercise sessions. All participants will complete an adverse event log, including pain scale, falls and any injuries before each study visit. [name] will be responsible for monitoring the study for patient safety and adverse events, and reviewing these logs on a daily basis. The DSMB will meet twice a year to review study progress and adverse events.

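### The log completed before each class prompts only for falls, injuries and pain, and no other scheduled prompt covers the rest of the protocol's own adverse event definition

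*Combined protocol and SAP*

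**What the plan says.** Section 7.3 defines an AE as "any unfavorable and unintended sign, symptom, injury or disease temporarily associated with an intervention or procedure" (the fourth-last word before the final phrase is printed that way), whether or not it is considered related. It adds that "information about AE determined to be unrelated to the study participation must be retained". Judging cause is the PI's task.

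Section 7.1 gives the routine instrument: before each visit, "participants will complete an adverse event log to monitor pain, falls, and any injuries". Section 7.6 repeats those three domains, and both sections have the PI review the logs daily. The matching form in Appendix III is the Hyperkyphosis Weekly Log. Its stems are "Have you fallen since the last group exercise class", "Have you had any injuries not related to a fall since the last group exercise class" and "Has your usual level of pain changed since the last class", followed by 0 to 10 pain ratings at rest and during movement, with body locations.

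Section 7.6 adds two further routes: a weekly opportunity to "privately discuss any musculoskeletal or other physical complaints due to study exercise", and a telephone number for reporting possible AEs between visits. Appendix III also holds an AE Report Form, which opens with a general question about any AE during the study, and an SAE Report Form, which has a hospitalization category.

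**The concern.** The definition covers four kinds of event: sign, symptom, injury and disease. The log covers injury, and covers symptoms only where they are pain. A participant can attend all 72 classes, answer every log truthfully with No, and still have had an illness, palpitations or an emergency visit that meets the 7.3 definition.

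Several parts of the plan rely on complete capture. The annual report is to list all AEs and compare their rates with pre-study assumptions (7.2). Any AE goes to the DSMB chair and the IRB within 48 hours (7.4). Stopping for harm rests on the estimated excess risk of observed adverse effects (section 8).

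The strengthening arm progresses to a Borg rating of 15-17. The screening forms already ask about chest pain and shortness of breath on exertion, so the investigators regard such symptoms as relevant at entry. Participants cannot be blinded. Where reporting is left to initiative, the two arms could report differently. Section 9.3 itself asks the DSMB to weigh ascertainment bias arising from different treatment regimens.

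**Working it through.** No arithmetic applies. The check sets the definition beside the form, then looks for any other scheduled prompt.

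**Step 1: identify the log.** No form in the appendix carries the title of AE log. The Weekly Log has fields for class and wave number, looks back to the last class, and has exactly the three domains that 7.1 and 7.6 name. It is taken to be that log.

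**Step 2: definition against log.**
- Injury: covered, by the fall stem and the non-fall injury stem.
- Symptom: covered only if it is pain. The pain locations include a free-text other entry.
- Sign: no item.
- Disease: no item.
- Unplanned medical visit or hospital stay: no item, although hospitalization is a category on the SAE form.

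The count is 3 domains, with 0 items on illness, non-pain symptoms or health-care contact.

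**Step 3: other scheduled prompts.** The Procedures Schedule has no row for AE assessment or for the AE form. Medical history and current medications appear only at the telephone and medical screens. The quality-of-life questionnaires at baseline, 6 months and 1 year touch on general health, fatigue and pain, but they are outcome measures, and nothing routes their answers to AE review.

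**Step 4: unscheduled routes.**
- Staff observation: real, but limited to what shows during a visit.
- Weekly talk: an opportunity rather than a question, and confined to complaints due to the exercise. That asks the participant to make the attribution that 7.3 gives to the PI.
- Contact number: open in scope, but depends on the participant calling.
- AE Report Form: open in scope, but worded in the third person for staff to complete, with no stated occasion for asking the participant.
- SAE form: records an admission once staff know of it.

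**Step 5: test cases.** A faint that causes a fall is caught by the fall stem. Chest pain can be entered as another pain location. Pneumonia, palpitations, breathlessness away from class, or an emergency visit for blood pressure would prompt no Yes on the log, unless accompanied by pain, a fall or an injury.

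**The case against.** The strongest reply is that the log is not the whole safety system. The AE Report Form asks about any AE, the SAE form records hospital stays, and the PI must evaluate every AE as it occurs, not just those on the log. Classes run with no more than 5 participants per teacher and are led by a licensed physical therapist, so a collapse or marked breathlessness in class would be seen. Three classes a week also make a serious illness likely to show as absence, and attendance is tracked.

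Much of this stands. A reader might infer that events outside the three domains are never asked about, or become known only if the participant volunteers them. The documents do not support either reading, because the open AE question and staff observation are both there. What these routes lack is a schedule: no visit is named for the open question, staff see only what happens in front of them, and the plan requires reasons for dropouts (7.2) but does not say that reasons for single absences are recorded.

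A second reply is that the log's focus fits the evidence. Section 2 reports musculoskeletal complaints in many studies and no serious exercise-related events across 121 trials. That justifies asking about falls, injuries and pain. It does not reconcile the log with a definition that ignores relatedness and requires unrelated AEs to be kept.

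A third reply is that differential reporting between arms is conjecture. That is fair. It is a possibility in an open-label trial, not something the documents show, and the log and contact number are common to both arms.

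**Conclusion.** The point holds as a mismatch between definition and instrument: the log elicits part of what 7.3 counts as an AE, and no scheduled prompt elicits the rest. The routes that remain are genuine but unscheduled. The 7.3 definition requires some association with an intervention or procedure, but this does not close the gap, since events are to be counted whether or not they are judged related.

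It would be tempting to attach an expected number of missed hospital admissions. The documents give no event rate, and the eligibility criteria remove people with end-stage disease, uncontrolled hypertension and several other risks, so a rate for older people in general need not apply. No count is offered, and the conclusion does not need one.

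The conclusion rests on two assumptions: that the Weekly Log is the AE log of 7.1 and 7.6, and that no operating procedure outside these documents already schedules an open AE question. It concerns what is asked, not the timing of the log. It is a minor point and a cheap improvement; it does not affect the primary analysis.

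**What to change.** - Add two Yes/No items with free text to the log, worded identically in both arms: (1) any new or worse illness or symptom since the last class; (2) any unplanned doctor or emergency visit, or hospital stay, since the last class. A Yes opens the AE form and, where it applies, the SAE form.
- Amend 7.1 and 7.6 to say that the log covers AEs as defined in 7.3, not only pain, falls and injuries.
- Give the AE Report Form a row and a stated time in the Procedures Schedule, the same for both groups.

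The cost is two lines on an existing REDCap form, a sentence in each of 7.1 and 7.6, and one schedule row. The downside is a few more unrelated AEs for the PI to review and report.
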